## 5.1.3. Return to previous treatment

After collection of the last pharmacokinetic sample, subjects will resume their original levodopa– carbidopa regimens (i.e. Duodopa treatment). If the treatment must be interrupted due to adverse events during the infusion period the subject will revert to his/her previous continuous treatment with Duodopa within approximately one hour or as judged appropriate by the investigator.

## 5.1.4. Dosing groups

Subjects will for practical reasons be admitted to the phase I unit in Gothenburg for the treatment visits in groups of up to three subjects. When more than one subject is treated at the same

	Study code:	IPO-001
Clinical Study Protocol	Version No:	5.1
	Date:	26 MARCH
		2019

occasion, dosing will for safety reasons be initiated with approximately 10-30 minutes in between each subject.

#### 5.1.5. Labelling

Infudopa Active and Infudopa Buffer IntraV will be packed and labelled at Recipharm, Infudopa Buffer SubC will be packed and labelled at Unimedic, and Duodopa will be packed and labelled at Tamro, according to current EU Good Manufacturing Practice (GMP) guidelines for pharmaceuticals.

Each infusion vial/cassette will be labelled with study code, dosage form, strength, quantity, dosage instructions, name of investigator, expiry date, storage instruction, "for clinical study use only", address and telephone number to sponsor/investigator.

#### 5.1.6. Storage and handling

All study medication should be kept separately from other medications at the study site, and in a secure place under appropriate storage conditions as specified on the pack label and handled according to the manufacturer's instructions. Expiry dates for investigational products are according to label.

The study medication should be stored in a fridge (2°C–8°C). The temperature of the fridge will be monitored each week and recorded in a temperature log.

It is the investigator's responsibility to establish a system for handling the study drugs to ensure that it is correctly received and recorded and only dispensed to subjects in accordance with this protocol and manufacturer instruction.

#### 5.1.7. Drug accountability and treatment compliance

The medication provided for this study is for use only as directed in the protocol. All unused drugs will be accounted for and destroyed appropriately by study site personnel. The study personnel will account for all drugs dispensed. At the end of the trial, it must be possible to reconcile delivery records with records of usage and returned stocks.

#### 5.1.8. Medical device equipment

Two infusion pumps, each having a 50 to 60 mL syringe (Figure 2) have UV-protected polyethylene (PE) infusion lining to a mixing connector (a Y-connector). After the Y-connector there is a single UV-protected infusion line (approx. length 150 cm) ending in a fine pore filter (Figure 3). An exit line after the filter is connected to a cannula, suitable for s.c. or i.v. administration. Both pumps are driven with the same speed and are started at the same time. The system is always primed with the solutions by starting with a high speed (40 mL/h) until a small aliquot comes out from the cannula (this priming can be automatically set).

The system has been extensively tested in laboratory experiments by following the levels of levodopa and carbidopa including a breakdown product of carbidopa (DHPA) and physical stability measures. The results show that Infudopa fulfils demands of a pharmaceutical product, also during in-use conditions. Infudopa is protected worldwide by approved patents and patent applications.

	Study code:	IPO-001
Clinical Study Protocol	Version No:	5.1
	Date:	26 MARCH
		2019

### Figure 2, A and B

A: The syringe filled with (1): Infudopa Active or (2) Infudopa Buffer IntraV (i.v. administration) or Infudopa Buffer SubC (s.c. administration)

[figure not shown]

B: Two loaded syringes are started with the same speed, at the same time. See how infusion line set is connected in Figure 3.

Figure 3. Set-up of the syringes, Y-connector, long UV-protected infusion line (to reach from Y-connector to bed/chair), 0.2  $\mu$ M sterile filter (white colour), which then is connected to another type of Y-connector with two short infusion lines with two cannulas for s.c. (only one shown here) or i.v. injection to the subject. The two B Braun Infusomat Space syringe pumps (not shown) drive the two syringes at the same speed.

Study code:	IPO-001
Version No:	5.1
Date:	26 MARCH
	2019

#### 5.1.8.1. Specification of equipment

All medical device equipment is CE-marked.

The following medical device equipment will be used in the study:

- B Braun Mini-Spike Green filter, ref 4550242,

- 50 mL syringe B Braun Omnifix Luer Lock Solo, ref 4617509F,
- Carefusion SmartSite Extension Set (Y-connector), ref 20061E7D
- B Braun Original Perfusor Line 150 cm (UV-protect), ref 8723017,

- B Braun Sterifix 0.2 µm filter, ref 4099354, (at s.c. administration can also B Braun Intrapur 1.2 µm filter, ref 4099850, be used),

- BD Venflon 20G 1.0 x 32 mm catheter, ref 391452 with suitable extension line, for i.v administration or Infucare Cleo 90 needle, ref 2021-08, for s.c. administration

- Infucare Y-set (ref. 210580) with 3 Luer Lock connections for 2 Infucare Cleo 90 needles

Other CE-marked medical device equipment distal to the filter may be used and should in these cases be noted in the eCRF.

	Study code:	IPO-001
Clinical Study Protocol	Version No:	5.1
	Date:	26 MARCH
		2019

### 5.1.8.2. Setting up the administration system and selecting dosage rates on pumps

A detailed instruction in Swedish is available for connection the different parts of the system, priming the system, and setting pump rates (see Appendix A).

## 5.2. Concomitant medication

Medications that are considered necessary for the subject's safety and well-being may be given at the discretion of the investigators unless not specified in the exclusion criteria. Concomitant medication will be recorded in the eCRF. Regarding administration of Duodopa, refer to the Summary of Product Characteristics (Investigator's Brochure, section 10 Appendix - reference safety information (RSI)). Drugs given during study specific Duodopa abstinence and listed in the protocol for that purpose do not have to be entered as concomitant medication, but each administration is recorded in the eCRF.

# 6. STUDY MEASUREMENTS AND VARIABLES

## 6.1. **Primary variable(s)**

The steady-state plasma concentration of levodopa, the area under plasma concentration versus time curve (AUC), and the coefficient of variation (COV) for plasma concentrations during the dosage interval in the subjects are the primary efficacy variables of the study. Also refer to Table 8.

## 6.2. Secondary variable(s)

Adverse events and vital signs documentation, local tolerability scores at the injection site, and laboratory assessments will be secondary variables to evaluate the safety of the study medication with special aim on the local tolerability at the injection sites of i.v. and s.c. administration.

Bioavailability based on the area under plasma concentration versus time curve (AUC) will establish the bioavailability of levodopa and carbidopa given s.c. and as Duodopa compared to the i.v. administration.

The third secondary objective of the study is to compare the efficacy and other pharmacokinetics during a treatment day of s.c. and i.v. Infudopa versus Duodopa, and supporting variables will be video recordings, PKG, and other pharmacokinetic variables, including the peak to trough fluctuation (PTF), than those mentioned as primary variables (refer to section 8.3 for the pharmacokinetic variables).

Evaluation of video recordings will include the secondary efficacy variables percentage of ratings within the interval -1 to +1, that is, a clinically desirable, functional "on" state accepting mild parkinsonism or mild dyskinesia, and percentage of ratings within the intervals -3 to -2 (severe to moderate "off") and +2 to +3 ("on" with moderate to severe dyskinesia). In everyday practice, most subjects prefer being dyskinetic before being "off." However, severe choreatic dyskinesia may be incapacitating and painful. Therefore, a secondary analysis of the interval -1 to +2, including moderate dyskinesia, will also be used.

The PKG measures median BK, median DK, FDS and percent time with tremor (PTT) will be evaluated for both normal active daytime (9-18, which is the most commonly reported measure) and for the full treatment time except the first hour.

# 6.3. Biological sampling procedures

### 6.3.1. Handling, storage and destruction of biological samples

Blood samples will be saved in an IVO registered biobank at Sahlgrenska University Hospital (number 890) according to the biobank act (Biobankslagen SFS 2002:297). All samples will be coded/pseudonymized. Samples will be saved for twenty years and will be used to address the study questions. Subjects will be informed that they can leave the study without any explanation at any time and that they can request that the samples should be destroyed or become anonymized. The samples may become analysed outside EU/EES. Only study responsible persons will have access to collected samples. Disclosure of samples for purposes not described in the project can be done only with the permission of the affected ethics committee.

### 6.3.2. Total volume of blood per subject

The total volume of blood taken from each subject during the study is maximum 450 mL.

# 7. SAFETY

### 7.1. Definitions

## 7.1.1. Adverse event (AE)

An Adverse Event is any untoward medical occurrence in a subject or clinical investigation subject administered a medicinal product and which does not necessarily have a causal relationship with this treatment. An adverse event (AE) can therefore be any unfavourable and unintended sign (including an abnormal laboratory finding), symptom, or disease temporally associated with the use of a medicinal (investigational) product, whether or not related to the medicinal (investigational) product. The terms "infusion site reaction" and "catheter site reaction" are used as predefined skin AE when there is a possible or most likely relation to the locally infused drug or the implanted catheter. More specific terms (like "infusion site pain" or "infusion site erythema") can be used when such symptoms occur in isolation, whereas "reaction" is the preferred description of combinations of symptoms which follow a similar time course.

### Causality

The investigator is responsible for determining whether there is a causal relationship between an AE and the use of a medicinal product.

All AEs are categorized either as unrelated, possibly related or related, as defined below:

- **Unrelated**: the AE is not reasonable in relation to the use of the medicinal product, or another cause can itself explain the occurrence of the event.
- **Possibly related**: the AE may be explained by the medicinal product and the onset is reasonable in relation to the use of the medicinal product, however there is insufficient information to determine the likelihood of this possibility.

• **Related**: the AE is most likely explained by the medicinal product and the onset is reasonable in relation to the use of the medicinal product.

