## 7.1.2. Adverse drug reaction (ADR)

An ADR is a noxious and unintended response to a medicinal product related to any dose administrated. The phrase responses to a medicinal product means that a causal relationship between a medicinal product and an adverse event is at least a reasonable possibility, i.e. the relationship cannot be ruled out.

The definition covers also medication errors and uses outside what is foreseen in the protocol, including overdose, misuse and abuse of the product.

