### 8.4. Interim analysis

There has been an interim analysis of first 5 subjects in the study (Clinical Study Interim Report 2019-01-15). There will be a new interim analysis of PK and safety data after 4 completed subjects after the study has re-started. The number of 4 subjects for the interim analysis is because it will allow for reasonably adequate mean values of numerical variables and frequencies of distribution of binominal variables, including reasonable estimates of confidence intervals. The following data will be included in the interim analysis (see Table 1 and 2):

- Blood PK samples
- Inspection of local dermal area/scoring incl. photos
- Adverse events

A Board of the Interim Study Analysis will meet to discuss the results and conclude if the study should continue or not.

The possible outcomes the Board will evaluate, and the basis for the decisions are:

1. Are the plasma levels of LD following s.c. and i.v. too high or too low as compared to Duodopa at any time during the treatment, so a dosage adjustment is necessary? Decision rules:

- If the deviation from Duodopa is of a magnitude that is deemed clinically important, appropriate changes in the dosing protocol in the study will be considered.

- If the deviation from Duodopa at steady-state is larger than established limits for bioequivalence (80% - 125%), the appropriate changes in the dosing protocol will be made.

2. Is the local and systemic tolerance acceptable?

Decision rule:

If adverse events have occurred which, according to the committee, can be attributed to the study drug and make it ethically unjustifiable to pursue the trial, the trial will be stopped. However, the trial can continue after the appropriate changes have been made if it can be convincingly demonstrated that changes in the protocol, e.g. a change of infusion rate, infusion system, an increase in the number of subcutaneous infusion sites or other feasible actions, will mitigate the risk for further adverse events.

In case the dosage regimen is changed, or other major change is made to the Clinical Study Protocol (CSP) an amendment must be submitted to MPA and EC.

Only descriptive summary statistics will be performed. There will be no statistical hypothesis testing.

The members of the Board of the Interim Study Analysis are presented in Appendix C.

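### The definition of *Unrelated* overlaps *Possibly related* and contradicts the protocol's own adverse drug reaction threshold, so related events can be under-labelled

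*Protocol*

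**What the plan says.** Section 7.1.1 of the protocol, under Causality, sets a three-level scale: "All AEs are categorized either as unrelated, possibly related or related, as defined below".

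- *Unrelated* has two conditions joined by an or. The event is not reasonable in relation to use of the product, "or another cause can itself explain the occurrence of the event".
- *Possibly related* requires that "the AE may be explained by the medicinal product and the onset is reasonable in relation to the use of the medicinal product", and that "there is insufficient information to determine the likelihood of this possibility".
- *Related* requires that the product most likely explains the event, with reasonable onset.

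Section 7.1.2 then sets the threshold for an adverse drug reaction (ADR): "a causal relationship between a medicinal product and an adverse event is at least a reasonable possibility, i.e. the relationship cannot be ruled out".

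Two later rules use the relatedness judgement. Section 7.2.2 requires events considered related, as judged by a medically qualified investigator or the sponsor, to be followed until they resolve or stabilise. Section 7.2.3 has the investigator and the sponsor's medical expert each assess every SAE, and a finding of relatedness by either one is enough to send it down the SUSAR route.

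**The concern.** A causality scale with one label per event should put each event in one category, and its line between related and unrelated should match the line that defines an ADR. Neither holds here. The second condition for *Unrelated* asks only whether another cause could account for the event. It does not ask whether that cause is more likely, or whether the product has been excluded.

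This is a practical matter in this trial, because alternative causes are common. Subcutaneous infusion always involves needles, so pain or haematoma at the site has a mechanical explanation to hand. For systemic events, the levodopa-free night and the temporary dopamine agonists allowed in section 3.3.6 are alternatives. Local tolerability is the special focus of the safety objective (section 2.2). Section 1.4 says that the haematoma and pain seen in the first five patients were judged most likely due to the solution, and that the subcutaneous buffer was changed. Whether such reactions persist with the new buffer is a question the restarted trial should answer, and treatment is open label when the causality call is made.

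At stake are the relatedness label, the follow-up that depends on it, and the relatedness input to SUSAR classification.

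**Working it through.** No figure in the protocol is in question, so the check is a comparison of the definitions followed by a trace of what depends on the label.

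**Step 1. Apply each definition to three types of event.**

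| Event | *Unrelated* (7.1.1) | *Possibly related* (7.1.1) | ADR (7.1.2) |
|---|---|---|---|
| A. Product may explain it, onset reasonable, likelihood cannot be determined, no other cause | No | Yes | Yes |
| B. As A, but another cause can itself explain it | Yes, by the second condition | Yes | Yes |
| C. Onset incompatible with use of the product | Yes, by the first condition | No | No |

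Types A and C behave as intended. Type B meets two of three categories that are meant to be alternatives. *Possibly related* is silent on other causes, so it does not give way to *Unrelated*. No tie-break appears in section 7.1.1 or elsewhere.

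**Step 2. Compare with section 7.1.2.** That a second cause could suffice does not rule the product out. Type B therefore remains an ADR under 7.1.2 even when it is coded *Unrelated* under 7.1.1. The protocol does not say which causality categories make up the ADRs, so nothing settles the conflict.

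**Step 3. Trace what depends on the label.**

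- Recording: does not depend on it. Section 7.2.1 records all adverse events whether or not they are attributed to the product.
- SAE reporting: does not depend on it. Section 7.2.3 requires every SAE to be reported whatever its relationship to treatment.
- Summaries: section 8.2 restricts neither the adverse event nor the local tolerability summaries to related events.
- Count of related events or ADRs: depends on it directly.
- Follow-up under section 7.2.2: depends on it. The section also does not say whether events considered related include *Possibly related*. Section 7.2.1 provides for follow-up information as necessary, which is a weaker commitment.
- SUSAR classification: depends on it. Either assessor can call the event related, so the step fails only if both call it unrelated. Section 7.1.1 is the only causality scale that the protocol gives them.

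**The case against.** The strongest reply is that this is a drafting point with limited reach. The word *itself* asks for a sufficient cause, not a merely conceivable one. An event that the product most likely explains has its own category. Section 7.1.2 states the reasonable-possibility standard shortly afterwards, and a careful assessor would apply it. Follow-up and SUSAR classification both bring in the sponsor's judgement. Safety is summarised descriptively, so no hypothesis test is affected. All of this is fair and limits the consequence. None of it tells the assessor what to do with a type B event, and a sufficient alternative cause still does not exclude the product.

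Several stronger readings are tempting, but the protocol does not support them.

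- *Drug reactions drop out of the safety data.* They do not. All adverse events and SAEs are captured regardless of causality, and no summary is confined to related events.
- *Infusion-site counts fall.* Section 7.1.1 applies the predefined site terms "when there is a possible or most likely relation to the locally infused drug or the implanted catheter", so an event blamed on the needle or catheter can still qualify. Section 3.3.7 has skin symptoms rated at set times, visual analogue ratings by subjects, and photographs scored by two blinded dermatologists, none of it filtered by causality.
- *The label controls what reaches the Board.* Under section 8.4 the Board receives the adverse events, dermal scoring and photographs, and decides for itself whether events "can be attributed to the study drug and make it ethically unjustifiable to pursue the trial".
- *Rows of related events in the safety tables are distorted.* Section 8.2 names only a standard set of tables. Any table by relationship would belong to an analysis plan that is not at hand.
- *The share of reactions lost can be given.* It would equal whatever proportion one assumed to have an alternative cause, and the protocol offers no basis for choosing one.

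**Conclusion.** The point holds in a limited form. Section 7.1.1 allows *Unrelated* for an event that the product may also explain with reasonable onset. This overlaps *Possibly related* without a tie-break and contradicts the ADR threshold in section 7.1.2.

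The result is misclassification within a complete safety record. Related events and ADRs can be under-counted, section 7.2.2 follow-up can be lost for non-serious events, and a SUSAR could be missed if both assessors apply the same wording. The number of events affected cannot be derived from the protocol. The conclusion rests on the ordinary reading of the or in the *Unrelated* definition, and on assessors applying that definition as written. The effect is modest, but this is a stated rule at odds with the protocol's own definition, not missing detail, and it should be corrected.

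**What to change.** Reconcile sections 7.1.1 and 7.1.2 with three changes.

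1. Limit *Unrelated* to events for which a causal relationship to the product can be ruled out, meaning that there is no reasonable possibility of one.
2. State that an event with both a plausible product cause and a plausible alternative is *Possibly related*.
3. State that *Possibly related* and *Related* together are the ADRs of section 7.1.2 and the events that section 7.2.2 means by considered related.

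The cost is a few sentences in the protocol and the matching help text in the eCRF. Design, sample size and assessments do not change. The downside is that counts of related events may be somewhat higher.

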#### Severity

In addition to assessing the relationship of the administration of the investigational product(s) to adverse events, an assessment is required of the intensity (severity) of the event. The following over-all classifications should be used:

- **Mild:** An adverse event which is relatively mild and transient in nature, but can be an annoyance, and does not interfere with normal activities.
- **Moderate:** An adverse event which may be uncomfortable but is not hazardous to health. It may be sufficiently discomforting to interfere with normal activities but does not completely prevent them.
- Severe: An adverse event which is incapacitating and/or it is a hazard to the subject.

## 7.1.2. Adverse drug reaction (ADR)

An ADR is a noxious and unintended response to a medicinal product related to any dose administrated. The phrase responses to a medicinal product means that a causal relationship between a medicinal product and an adverse event is at least a reasonable possibility, i.e. the relationship cannot be ruled out.

The definition covers also medication errors and uses outside what is foreseen in the protocol, including overdose, misuse and abuse of the product.

### 7.1.3. Serious adverse event (SAE)

Any untoward medical occurrence or effect that at any dose:

- results in death,
- is life-threatening,
- requires inpatient hospitalization or prolongation of existing hospitalization,
- · results in persistent or significant disability/incapacity, or
- is a congenital anomaly/birth defect

Medical and scientific judgement should be exercised in deciding whether an event is 'serious' and if expedited reporting is appropriate in other situations, such as important medical events that may not be immediately life-threatening or result in death or hospitalization, but may jeopardize the subject or may require intervention to prevent one of the other outcomes listed in the definition above. These events should also usually be considered SAEs.

